8.4 Reporting Procedures – Notifying the IRB

8.4.1 Adverse Event Reporting

Unexpected AEs which are possibly related, probably related, or definitely related will be reported to the IRB using the Reportable New Information (RNI) tool within Research Navigator within 48 hours of study team awareness.

All other AEs will be documented in the AE/SAE log to be submitted to the IRB at the time of annual continuing review.

8.4.2 Serious Adverse Event Reporting

Unexpected SAEs which are possibly related, probably related, or definitely related will be reported to the IRB using the Reportable New Information (RNI) tool within Research Navigator within 48 hours of study team awareness.

All other SAEs will be documented in the AE/SAE log to be submitted to the IRB at the time of annual continuing review.

CONFIDENTIAL

This material is the property of the NYU School of Medicine and Langone Medical Center. Do not disclose or use except as authorized in writing by the study sponsor
Interventional Template Version: 11 January 2019

8.4.3 Unanticipated Problem Reporting

Incidents or events that meet the OHRP criteria for UPs require the creation and completion of an UP report form. It is the site investigator's responsibility to report UPs to their IRB. The UP report will include the following information:

- Protocol identifying information: protocol title and number, PI's name, and the IRB project number;
- A detailed description of the event, incident, experience, or outcome;
- An explanation of the basis for determining that the event, incident, experience, or outcome represents an UP;
- A description of any changes to the protocol or other corrective actions that have been taken or are proposed in response to the UP.

To satisfy the requirement for prompt reporting, UPs will be reported using the following timeline:

- UPs that are SAEs will be reported to the IRB within 24 hours of the investigator becoming aware of the event.
- Any other UP will be reported to the IRB within 24 hours of the investigator becoming aware of the problem.
- All UPs should be reported to appropriate institutional officials (as required by an institution's written reporting procedures within 24 hours of the IRB's receipt of the report of the problem from the investigator.

8.5 Study Halting Rules

Administration of study agents will be halted and the study will be discontinued if the PI determines that 3 unexpected and related (possibly related, probably related, or definitely related) AEs have occurred.

8.6 Safety Oversight

It is the responsibility of the Principal Investigator to oversee the safety of the study. This safety monitoring will include careful assessment and appropriate reporting of adverse events as noted above. Medical monitoring will include a regular assessment of the number and type of serious adverse events.

Data Safety Monitoring

The PI is responsible for conducting systematic and periodic reviews of aggregate data and adverse events in accordance with the data safety monitoring plan. In addition to reviewing AEs, the PI will review assessments of drain site, pain scores, and opioid usage in order to ensure safety of enrolled subjects.

The PI will review all study data and adverse events throughout the study on an annual basis. Administration of study agents will be halted and the study will be discontinued if the PI determines that 3 unexpected and related (possibly related, probably related, or definitely related) AEs have occurred.

A summary of the outcomes of these safety reviews along with accumulated adverse events and deviations will be submitted to the IRB as part of an annual progress report at the time of the Continuing Review submission.

9 Clinical Monitoring

Clinical site monitoring is conducted to ensure that the rights and well-being of human subjects are protected, that the reported trial data are accurate, complete, and verifiable, and that the conduct of the trial is in compliance with the currently approved protocol/amendment(s), with GCP, and with applicable regulatory requirement(s).

CONFIDENTIAL

This material is the property of the NYU School of Medicine and Langone Medical Center. Do not disclose or use except as authorized in writing by the study sponsor
Interventional Template Version: 11 January 2019

Individual subject monitoring for this study will be performed by the PI in an ongoing basis as patients are undergo routine clinical follow-up assessments of their drain sites. We review these clinical assessments and add them to our study data. There are no additional assessments of safety that the patient will need to undergo as part of this study.

10 Statistical Considerations

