5.4 Strategies for Recruitment and Retention

Patients will be prospectively recruited after IRB approval until a total of 10 patients are enrolled and randomized in each study group for a total of 40 patients. We believe this process will take approximately 2-3 months.

Patients will be recruited from investigator and sub-investigator clinical practices, during each patient's pre-operative visit for elective hand surgery.

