5.5 Duration of Study Participation

Pre-operative visit will occur up to 3 months prior to surgery. Final Study visit will occur up to 6 weeks after surgery. Primary endpoint (returning completed pain diary to study staff) occurs at Day 14. Participants

CONFIDENTIAL

This material is the property of the NYU School of Medicine and Langone Medical Center. Do not disclose or use except as authorized in writing by the study sponsor
Interventional Template Version: 11 January 2019

remain enrolled in the study up until their standard of care post-op visit, which typically occurs 4-6 weeks after surgery. Participation is complete when participants complete their final standard of care post-op visit.

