6.1.3 Route of Administration

Study drugs are applied topically to surgical bed prior to closure of skin.

7 Study Procedures and Schedule

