7.1 Study Procedures/Evaluations

7.1.1 Study Specific Procedures

Patients meeting inclusion criteria will be randomized at their preoperative appointments with a sealed envelope method and an initial evaluation will be completed for pre-operative pain levels using the numerical pain rating scale. At the conclusion of their respective surgery just prior to wound closure, the appropriate medications will be topically administered into the wound and the wound will be closed via standard method. Patients will record pain scores at home daily and also record the amount of pain pills (Norco 5/325mg) needed postoperatively until post operative day 14.

Preoperative analog pain scoring will be performed followed by postoperative analog pain scoring on postoperative day 0-14. Compliance will be recorded by the patient in a written form. Number of opioid pain medications taken will also be recorded by patient in a written form.

Analog pain scoring preoperatively on day of surgery and postoperatively day of surgery. Pain scale from 0 (no pain) to 10 (highest level of pain ever experienced). This scoring system will also be utilized by the patient daily until postoperative day 14.

Opioid prescriptions (Norco 5/325 mg) will be given to patients post operatively. Total number of pills taken up until post operative day 14 will be recorded by the patient.

This will allow us to track the patients relative pain pre and postoperatively until postoperative day 14.

- Medical history will be obtained in hand surgery clinic at initial patient presentation.

CONFIDENTIAL

This material is the property of the NYU School of Medicine and Langone Medical Center. Do not disclose or use except as authorized in writing by the study sponsor
Interventional Template Version: 11 January 2019

- Medication history will include details about the specifics of their hand problem along with a past medical history that includes history of chronic pain, narcotic addiction, recreational drug dependency, psychiatric pathologies, allergy to drugs and preferences for anesthesia. Those patients who only wish to have an anesthetic upper extremity block performed by anesthesia will not qualify for the study.
- Physical examination will consist of a full hand examination. The most important criteria will be the presence or absence of an already open wound prior to surgical intervention.

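### The only stated interval for the PI's aggregate safety review is annual, but on the planned timeline all 40 patients are treated by about month 6

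*Combined protocol and SAP*

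**What the plan says.** Section 8.6 (Safety Oversight) makes the PI responsible for safety and sets the frequency of the overall review: "The PI will review all study data and adverse events throughout the study on an annual basis". It describes this oversight as a means of keeping enrolled subjects safe. The sentence after the frequency repeats the rule in section 8.5: "Administration of study agents will be halted and the study will be discontinued if the PI determines that 3 unexpected and related" adverse events have occurred.

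Section 8.6 also mentions repeated reviews of pooled data under a data safety monitoring plan, and a regular look at the number and kind of serious adverse events. It gives no interval for either.

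The schedule comes from other sections. On recruitment, section 5.4 says: "We believe this process will take approximately 2-3 months". Section 5.5 says: "Pre-operative visit will occur up to 3 months prior to surgery" and "Final Study visit will occur up to 6 weeks after surgery". Treatment is a single application in the operating room (6.1.3): "Study drugs are applied topically to surgical bed prior to closure of skin". The Protocol Summary gives a study duration of 12 months.

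**The concern.** A review of accumulated safety data protects participants only if some are still to be treated when it takes place. Each patient here is treated once, at surgery, and the planned treatment period is short. An annual review suits a trial with long accrual or continuing dosing. In this one, its first occurrence coincides with the planned end of the study.

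At stake is the aggregate view: whether related events are gathering in one arm, at one site or over time. The halting rule needs a count over all patients, and a stated review during treatment is the natural place to make that count.

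**Working it through.** **Inputs**
- Sample size: 4 arms × 10 = 40, which reproduces the total in section 5.4.
- Recruitment: 2-3 months (5.4), a planning estimate.
- Randomization takes place at the pre-operative visit (7.1.1): "Patients meeting inclusion criteria will be randomized at their preoperative appointments with a sealed envelope method". The wait for surgery therefore comes after enrolment and adds to the recruitment period.
- Wait from that visit to surgery: 0 to 3 months (5.5).
- Final visit: up to 6 weeks after surgery (5.5). 6 weeks = 42 days ÷ 30.4 ≈ 1.4 months.
- First annual review: month 12, assuming the clock starts near first enrolment.

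**Last surgery = recruitment length + wait**
- Longest case: 3 + 3 = month 6.
- Two-month recruitment, longest wait: 2 + 3 = month 5.
- No wait: month 2 to 3.

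**Last visit = last surgery + 6 weeks**
- Longest case: 6 + 1.4 = month 7.4, or about 7.5 if six weeks is counted as a month and a half.

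**Distance to the review**
- From last surgery: 12 − 6 = 6 months.
- From last visit: 12 − 7.4 = 4.6 months.
- Patients treated before the review: 40 of 40.

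**How far the plan would have to slip**
- With the longest wait, a surgery falls after month 12 only if recruitment runs beyond 12 − 3 = 9 months, three times the upper end of the plan.
- Even with 12 months of even recruitment and a 3-month wait for everyone, (12 − 3) ÷ 12 × 40 = 30 patients would have been treated by the review.
- If the annual clock ran from IRB approval, first enrolment would have to come more than 12 − 6 = 6 months after approval for the review to precede the last surgery in the longest case.

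**Whether other sections supply an earlier aggregate count**
- 8.2.2 and 8.2.3: the examining clinician grades causality and the PI decides expectedness. Both judgments are needed before an event counts toward halting. No section says when they are brought together into a total.
- 8.4.1 and 8.4.2: unexpected related events go to the IRB within 48 hours, one event at a time.
- 9: the PI's ongoing monitoring is described as monitoring of individual subjects.
- 8.6: the regular assessment of serious events is a count over patients, but it has no interval and covers serious events only. The halting rule counts all unexpected related events.

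**The case against.** The strongest reply is that the halting rule does not depend on the annual review. Section 8.5 stands alone and applies whenever the PI finds that three qualifying events have occurred. Section 8.6 restates it without making it conditional on the review. The PI judges the expectedness of each event, and the events that count toward halting are those reported within 48 hours. In a 40-patient trial, an attentive PI would probably notice the third. Section 5.8 separately allows suspension for unacceptable risk at any time. The data safety monitoring plan, which is not among the documents, may set a shorter interval.

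Most of this stands, and it limits the point. A reader might infer that halting is considered only once no treatment is left to stop, or that the three-event rule is the trial's sole protection. The documents support neither: the rule is event-driven, and 5.8 gives a second, discretionary route. Nor can one say how many patients would be treated needlessly. The documents give no rate for unexpected related events, and such a figure would also require the count to be made only at the annual review, which the protocol does not say. The annual submission of other adverse events under 8.4.1 is no evidence of delay, because those events do not count toward halting.

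The reply does not supply an aggregate review during the treatment period. The one interval that the protocol states is longer than that period, and the running total is left implicit.

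**Conclusion.** The point holds in this limited form. The scheduled annual review falls about 6 months after the last planned surgery and 4.6 months after the last visit, when all 40 patients have been treated. It therefore cannot serve the protective purpose that section 8.6 gives it. Earlier action is possible through event-by-event assessment, 48-hour reporting and section 5.8, but no section requires a cumulative count of qualifying events across patients and sites while treatment is under way.

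Two assumptions carry the result: recruitment stays within 9 months (the plan is 2-3), and the annual clock starts near first enrolment. Month 6 is an upper bound derived from the plan's own intervals. The documents do not state a date for the last surgery. The change is worth making because it is cheap and replaces a stated interval that does not fit the timeline.

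**What to change.** Reconcile the review interval in section 8.6 with the recruitment and surgery timeline:

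1. Replace the annual interval for the PI's review with one shorter than the treatment period, for example after about every 10 treated patients. With 40 patients this gives 40 ÷ 10 = 4 reviews, three of them (after 10, 20 and 30) while patients remain to be treated.
2. State that the PI updates the cumulative count of unexpected related adverse events, over all patients and both sites, whenever one is reported under section 8.4.
3. If the data safety monitoring plan already sets a shorter interval, cite it in 8.6 so that the two agree.

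The halting threshold is unchanged and no rule on holding treatment is added. The annual summary to the IRB can stay as a reporting requirement. The cost is protocol wording and about four short PI reviews, with no extra staff.

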10.1 Statistical and Analytical Plans (SAP)

10.1.1 General Approach

Each arm of this randomized, single-blinded, placebo-controlled study will have a minimum of 10 patients. There will be a minimum of 40 patients in the study. Patients will be randomized using Microsoft Excel.

Simple randomization will be used to determine the treatment arm. In order for us to power our study based on a previous similar study at NYU for topical application (Haddock et al., Thrombin and Topical Local Anesthetic for Postoperative Pain Management), we will need 10 patients for each individual treatment arm to detect any difference in the outcome.

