Brief Summary	
This study is a prospective randomized trial examining the effect of tranexamic acid (TXA) and aminocaproic acid (ϵ-Ahx) with local anesthetics and thrombin in all electively created surgical wound beds in hand surgery to provide long term pain relief and decrease the use of postoperative narcotics.
 
All surgical created wounds for any hand surgery will be treated in a randomized fashion with the following four arms:
 
1. Bupivacaine + lidocaine2. Bupivacaine + lidocaine + thrombin3. Bupivacaine + lidocaine + thrombin + tranexamic acid4. Bupivacaine + lidocaine + thrombin + aminocaproic acid 
All are applied topically to surgical bed prior to closure of skin.

Phase	N/A
Objectives	
The primary objective of this study is to evaluate the effectiveness of topical antifibrinolytics, thrombin and local anesthetics on postoperative pain control in patients undergoing elective hand surgery. We want to determine the efficacy of this treatment over treatment with thrombin and local anesthetics and just local anesthetics alone to the same population of patients.
 
The secondary objective of the study is to reduce the amount of opioid pain medications required postoperatively for routine hand surgery procedures.

Methodology	Prospective single blinded study
Endpoint	Degree of pain and amount of adjuvant pain medication used at 1 month post surgery
Study Duration	12 months
Participant Duration	Pre-operative visit occurs up to 3 months prior to surgery Final Study visit occurs up to 6 weeks after surgery. Primary endpoint (returning completed pain diary to study staff) occurs at Day 14. Participants remain enrolled in the study up until their standard of care post-op visit, which typically occurs 4-6 weeks after surgery. Participation is complete when participants complete their final standard of care post-op visit.
Duration of IP administration	Applied topically to surgical bed prior to closure of skin
Population	Nontraumatic, elective upper extremity (hand) surgery cases, age 18 or older
Study Sites	NYU Langone Health Bellevue Hospital Center
Number of participants	40 (10 per study arm)
Description of Study Agent/Procedure	Applied topically to surgical bed prior to closure of skin: 1. Bupivacaine + lidocaine (reference therapy) 2. Bupivacaine + lidocaine + thrombin 3. Bupivacaine + lidocaine + thrombin + tranexamic acid 4. Bupivacaine + lidocaine + thrombin + aminocaproic acid

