5.6 Total Number of Participants and Sites

Patients will be recruited from NYU Langone Health and from Bellevue Hospital Center.

Recruitment will end when approximately 40 participants are enrolled. It is expected that approximately 40 participants will be enrolled in order to produce 40 evaluable participants.

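### Simple randomisation does not deliver the stated 10 patients per arm at about 40 patients: all four arms reach 10 in 0.39% of allocations at 40 and 9.7% at 44

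*Combined protocol and SAP*

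**What the plan says.** Section 10.1.1 names the method: "Simple randomization will be used to determine the treatment arm". It adds that the randomisation is done in Microsoft Excel. The same section sets the size: "Each arm of this randomized, single-blinded, placebo-controlled study will have a minimum of 10 patients" and "There will be a minimum of 40 patients in the study". It says that 10 per arm are needed to detect a difference, with reference to an earlier study at the institution.

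Other sections treat 40 as the total, not as a floor. The Protocol Summary gives the number of participants as "40 (10 per study arm". Section 5.4 recruits "until a total of 10 patients are enrolled and randomized in each study group for a total of 40 patients". Section 5.6 says "Recruitment will end when approximately 40 participants are enrolled" and then "It is expected that approximately 40 participants will be enrolled in order to produce 40 evaluable participants".

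The schematic and sections 7.1.1 and 7.2 say that allocation is by sealed envelope at the preoperative visit. The available text does not mention blocks, a balanced set of envelopes, a cap on an arm, or replacement of patients. Section 5.7.1 allows withdrawal, and 10.1.2 takes patients with missing diary data out of the analysis.

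**The concern.** Under simple randomisation each patient is assigned independently, so arm sizes vary by chance. A plan that uses it can fix the total, or it can recruit until each arm is full, but it cannot expect both 10 per arm and 40 in total. As written, either some arms end below 10 when recruitment stops at about 40, or recruitment runs well past 40.

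Ten per arm is the only sample-size requirement in the plan. Whether it is met, and how large the arms are in any one comparison, depends on the allocation that happens to be drawn. This is avoidable without enrolling one more patient.

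**Working it through.** **Inputs.** Four arms (4.1); at least 10 per arm and at least 40 in total (10.1.1); 40 at 10 per arm (summary, 5.4); stop at about 40 (5.6). Assumption: probability 1/4 per arm. The plan states no ratio, but the equal targets imply it.

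**The plan's own figure.** 4 × 10 = 40, so the totals agree arithmetically. The power basis for 10 per arm cannot be reproduced, because no effect size, SD, event rate or power is given. The check below does not need one.

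**Chance that every arm has at least 10.** At N = 40 the only qualifying split is 10/10/10/10, so

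P = 40! / [(10!)⁴ × 4⁴⁰] = 4.705 × 10²¹ / 1.209 × 10²⁴ = 0.00389, or 0.39%.

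At N = 41 one arm has 11 and the others 10:

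P = 4 × 41! / [11! × (10!)³ × 4⁴¹] = 0.0145.

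For larger N, the multinomial probabilities of all splits with every arm at 10 or more are summed exactly:

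| N | P(every arm ≥ 10) |
|---|---|
| 40 | 0.39% |
| 41 | 1.5% |
| 44 | 9.7% |
| 48 | 29.9% |
| 52 | 51.9% |
| 65 | 91.3% |

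The value 44 is 10% above 40. It illustrates about 40 and is not a figure from the plan. In 2,000,000 simulated allocations the proportions were 0.38% at 40 and 9.7% at 44.

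**How short the arms fall at N = 40.**
- P(smallest arm ≥ 8) = 0.360, so some arm has 7 or fewer in 1 − 0.360 = 64.0% of allocations.
- The smallest arm averages 6.8 patients and the largest 13.3.
- A pre-named arm is Binomial(40, 0.25). It is below 10 with probability 44.0% and at 7 or fewer with probability 18.2%.

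**Recruiting until every arm has 10.** Expected total = 40 + Σ over N ≥ 40 of [1 − P(every arm ≥ 10 at N)] = 53.6, about 54 patients. The median is 52, because the probability first passes 50% there.

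**Effect on power (illustration only).** Take a two-sided t-test at 0.05 between two pre-named arms, with the effect set to give 80% power at 10 v 10. That effect is 1.325 SD. The noncentrality is 1.325 × √[n₁n₂/(n₁+n₂)]:
- 10 v 10: 1.325 × √5 = 2.96, power 80%.
- 7 v 10: 1.325 × √(70/17) = 2.69, power 71%.

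Averaged over all allocations at N = 40, power is 76.7%, a loss of 80 − 76.7 = 3.3 points. It is below 70% in 19% of allocations.

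**The case against.** **The headline percentage is severe.** At exactly 40, at least 10 in every arm can only mean a perfect split, so 0.39% measures failure to hit one target. A pre-named arm still has 8 or more in 1 − 0.182 = 82% of allocations. This is fair, and it is why the size of the smallest arm matters as well as the percentage. But the perfect split is what the plan states, and four patients above 40 still succeed in fewer than one allocation in ten.

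**The plan may mean something else.** Section 10.1.1 gives minima, 5.4 recruits until each group has 10, and sealed envelopes could be a prepared set with 10 per arm. The minima do allow more than 40, but 5.6 stops at about 40, and filling every arm under simple randomisation takes about 54. Closing an arm when it is full, or preparing a balanced set, would not be simple randomisation. If either is intended, 10.1.1 still needs correcting, and the percentages above would then not apply.

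**The power illustration is not the plan's primary analysis.** This stands. Section 10.1.2 uses two-proportion z tests for pain, Kruskal-Wallis for pills, and analysis of variance for PACU time, which is a secondary endpoint. The t-test figures show only the order of magnitude.

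**A reader might infer more.** One might conclude that unequal arms bias the comparison, or that the trial loses most of its power. Neither follows. Independent random assignment stays unbiased whatever the arm sizes, and on the illustrative test the average loss is about 3 points. The documents give no effect size, SD or power from which a larger loss could be shown.

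**Restriction makes assignments easier to guess.** This also stands, and it matters in a single-blinded study that recruits from the investigators' own practices. It is counted below as a cost.

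**Conclusion.** The inconsistency holds as the text is written: the stated method does not deliver the stated arm sizes at the stated total. The percentages rest on equal allocation probabilities and on the literal meaning of simple randomisation; the 9.7% also rests on reading about 40 as 44.

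The consequence is moderate. There is no bias, and the average loss of power is a few points, but a single comparison can fall well below the planned size. The point should be corrected because the remedy needs no extra patients.

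The statement in 5.6 that about 40 enrolled will give 40 evaluable has a related weakness. Sections 5.7.1 and 10.1.2 allow removals, and any loss falls on arms that may already be short. The documents give no loss rate, so no figure is put on this.

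**What to change.** In 10.1.1, replace simple randomisation with a restricted, concealed scheme that gives exactly 10 randomised per arm at 40. Either of these would do:
- one randomly ordered list of 40 assignments, 10 per arm; or
- permuted blocks of mixed, undisclosed size, ending at 40.

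Issue assignments centrally across both sites, for example through the existing REDCap system or by a call to the holder of the list. Separate envelope stacks at each site would not guarantee the balance. Bring the sealed-envelope wording in the schematic, 7.1.1 and 7.2 into line.

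Use one wording in the summary, 5.4, 5.6 and 10.1.1: 40 randomised, 10 per arm. In 5.6, stop equating 40 enrolled with 40 evaluable.

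**Cost.** A new list, central coordination of two sites, and some predictability. The table shows correct guesses out of 40 for a recruiter who sees all earlier assignments and always guesses the least-used arm. The two restricted schemes were simulated.

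| Scheme | Correct guesses of 40 |
|---|---|
| Simple randomisation | 40 × 1/4 = 10 |
| One shuffled list of 40 | about 14.7 |
| Mixed blocks of 4 and 8 | about 19.6 |

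Recruiters who see only their own site's assignments would do less well. On this measure the single shuffled list is the less predictable choice.

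The change secures 10 randomised per arm. It does not secure 10 analysed, which depends on how many patients are later removed.
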